6.7.2. Adverse Events

All SAEs will be collected from the signing of the ICF until the 8-week follow-up visit. All AEs will be collected from the first dose of study drug until 4 weeks after the last dose of study drug. All AEs recorded on the CRF will be coded using the latest MedDRA dictionary around the time of Database Lock and classified as either AEs or TEAEs as follows:

- TEAEs for Part A and Period 1 in Part B are either events with start date and time after the start of the Treatment Period and up to 4 weeks after the end of the Treatment Period (for subjects in Part A or those who don't enter Part B Period 2), or events with start date and time prior to the start of the Period 1 whose severity worsens on or after the start of Period 1 and up to 4 weeks after the end of the Treatment Period (for subjects in Part A or those who don't enter Part B Period 2).
- TEAEs for period 2 in Part B are either events with start date and time after the start of administration of Week 16 treatment and up to 4 weeks after the end of the Treatment Period, or events with start date and time prior to the start of administration of Week 16 treatment whose severity worsens on or after the start of administration of Week 16 treatment through 4 weeks after the end of the treatment period. For subjects who receive treatment in period 2, TEAEs with start date after the start of period 2 will be assigned to period 2 only, not to period 1.
- Treatment-Emergent Serious AEs (TESAEs) will be defined as TEAEs which meet the criteria as Serious = "Yes".
- The relationship between a TEAE and treatment is assessed as related or not related. A treatment-related TEAE will be defined as a TEAE considered by the investigator as related to treatment or with unknown/missing relationship to treatment.
- Assessment of AE intensity will be based on CRF AEs form. Severe TEAEs are defined as TEAEs assessed as being "Severe" in intensity and include those events where the intensity is missing.
- TEAEs leading to discontinuation of treatment are defined as TEAEs where "Action Taken with Study Treatment" is indicated as "Drug Withdrawn".
- Injection site reactions (ISRs) will be defined as any adverse event where the preferred term contains the words "injection site".

In addition to the aforementioned AE types, the following TEAEs of special interest will be summarized:

- Candida infection,
- Inflammatory bowel disease,
- Suicidal ideation.
- Malignancies
- Major adverse cardiovascular and cerebrovascular events (cerebrovascular accident and transient ischemic attack, non-fatal myocardial infarction or unstable angina, and cardiovascular death)
- Tuberculosis
- Infections (opportunistic, serious, or fungal only)
- Cytopenias
- Systemic hypersensitivity reaction

Adverse events of special interest will be identified manually. After all data are entered into the database and before database unblinding, a list of all unique PTs will be generated. ACELYRIN pharmacovigilance and clinical development representatives will review the list and determine which are TEAEs of special interest in each category listed above. This determination will be documented in a memo, signed and dated after database lock and prior to unblinding for the primary analysis (and after final database lock for the final analysis), and stored in the study trial master file. The memo will specify the subjects and preferred terms to be included as TEAEs of special interest, including justification for including or excluding events as appropriate. The database will not be unblinded until the memo is finalized and signed.

Adverse events will be summarized by default descriptive summary statistics for categorical variables for the Safety Analysis Set as follows:

- An overview of TEAEs including the number and percentage of subjects with at least one of each mentioned TEAE type:
 - Any TEAE
 - Leading to discontinuation of study drug
 - Mild
 - Moderate
 - Severe
 - Any moderate or severe AE
 - Any study treatment related TEAE
 - Leading to discontinuation of study treatment
 - Any serious TEAE
 - Leading to discontinuation of study treatment

- Leading to death
- Any serious study treatment related TEAE
 - Leading to discontinuation of study treatment
 - Leading to death
- The number and percentage of subjects reporting each TEAE and the count of number of events will be summarized by SOC and PT for the following types of TEAEs.
 - TEAEs of Special Interest
 - TEAEs Leading to Discontinuation of Study Treatment
 - TEAEs by Maximum Severity
 - TEAEs by Relationship to Treatment
 - TEAEs by Relationship and Maximum Severity
 - Study Treatment related TEAEs
 - Study Treatment Related TEAEs Leading to Discontinuation of Study Treatment
 - Serious TEAEs
 - Serious TEAEs Leading to Discontinuation of Study Treatment
 - Serious TEAEs Leading to Death
 - Study Treatment Related Serious TEAEs
 - Study Treatment Related Serious TEAEs Leading to Discontinuation of Study Treatment
 - Study Treatment Related Serious TEAEs Leading to Death
- The number and percentage of subjects reporting each TEAE and the count of number of events will be summarized by SOC and PT for two subgroups:
 - Subjects < 65 years of age at baseline
 - Subjects \geq 65 years of age at baseline
- The number and percentage of subjects who died will be summarized
- The number and percentage of subjects reporting each TEAE and the count of number of events will be summarized by descending incidence PT (by total group) for the following types of TEAEs.
- All TEAEs
- TEAEs of Special Interest

In the above summaries, subjects with more than one TEAE within a particular SOC are counted only once for that SOC. Similarly, subjects with more than one TEAE within a particular PT are counted only once for that PT.

For summaries by maximum severity, subjects with multiple TEAEs within a particular SOC or PT will be counted under the category of their most severe TEAE within that SOC or PT. TEAEs with missing severity will be included in the counts as severe.

Summaries by SOCs and PTs will be sorted by SOCs by their Internationally Agreed Order (MedDRA) and PTs within SOC by descending order of total incidence. Where PTs tie, PTs will be sorted alphabetically. Summaries by PTs only will be sorted by descending order of total incidence.

All AE data will be listed and AEs and TEAEs will be presented together. Treatmentemergence status will be flagged in the listing. The listing will present the relative start and stop day of the AE calculated relative to the first dose of treatment and will be presented for those subjects who received at least one dose of treatment. If the AE is "Ongoing" it will be indicated as such in the listing and the relative stop day will not be calculated. Only original dates will be presented in the listing even though the relative day may be based on an imputed date.

AESIs and ISRs will be summarized for by treatment group, SOC, and PT. A similar summary will be provided by PT only for ISRs. These tables will be presented for the whole study period as well as by period (Period 1 and Period 2, separately, for Part B). Only subjects who have at least one dose of study drug in Period 2 are included in the summaries during Period 2.

To assess the pattern of initial onset, AESIs and ISRs will also be presented by Kaplan-Meier plot. This summary will be done for the full study period and, separately, only for Period 2. For the Period 2 summary, the day of onset will be calculated with respect to the Week 16 date of dosing (Date of AE - Date of Week 16 dose + 1).

Separate Kaplan Meier (KM) plots will be created for the study duration and Period 2 for time to:

- First onset of an event in each AESI category
 - If an AESI category has < 3 events in a treatment arm, then this analysis will not be done.
 - Subjects who do not experience an event will be censored at their date of last contact.
- First ISR
 - Subjects who do not experience an event will be censored at the date of their last injection.

The date/time of onset of the first instance of the event of interest (AESIs or ISRs) will be used as the date/time of the event in the analysis.

The product limit estimator will be presented by treatment group for Week 4 (Day 28), Week 8 (Day 56), Week 12 (Day 84), Week 16 (Day 112), Week 20 (Day 140), Week 24 (Day 168), Week 28 (Day 196), and Week 32 (Day 224) for each AESI category and for ISRs.

Incidence of ISRs will be summarized for the whole study period by treatment group, and injection visit week (Day 1, Week 1, Week 2, etc). If a subject didn't have an injection at the visit week, they will not be counted in the denominator for the incidence calculation.

A similar presentation of ISRs by treatment group and injection visit week will also be done, but the cumulative number of ISRs up to the injection visit week will be summarized at the visit week. This summary will be done for the full study period as well as by treatment period.

An overall summary of ISRs will be produced by treatment group, Period 1, Period 2, and for the full 32 week treatment period. The summary will include the number of subjects with:

- ISRs leading to discontinuation
- ISR at each maximum intensity/severity
- Related ISRs
- Serious ISRs
- Serious related ISRs

An ISR is considered to correspond to a particular visit week if it occurs on or after the indicated injection visit date/time, and prior to the next inject visit date/time. If no subsequent injection visit date/time is available, then the ISR will correspond to the closest injection visit date occurring prior to it.

To evaluate the pattern of subjects experiencing multiple ISRs in Period 1 of the study (or the full treatment period in Part A), the number and percent of subjects with ISRs on or after Day 29 (through the end of the period) will be presented by the four treatment groups and by the following subgroups:

- Subjects who had at least one ISR on Days 1-28
- Subjects who had no ISRs on Days 1-28

A similar analysis by the four treatment groups will be presented for Period 2 Part B, where the two subgroups of interest are:

- Subjects who had at least one ISR up to Week 16
- Subjects who had no ISRs up to Week 16

ISRs will also be graphically presented by treatment group using a lasagna plot. The y-axis will be each injection visit week, the x-axis will represent each subject, and each 'square' on the plot will be color coded into the following categories: missing injection, no ISR at the visit, mild, moderate, and severe ISRs. The lasagna plot will be presented by treatment group, and sorted by ISR first onset and severity (earliest and most severe will be sorted at the top).

In addition, the following listings will be presented:

- Listing of Deaths
- Listing of TEAEs
- Listing of Serious TEAEs
- Listing of AEs Leading to Interruption of Study Treatment
- Listing of AEs Leading to Discontinuation of Study Treatment
- Listing of AEs of Special Interest

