6.6.7. Post-Week 16 (Part B, Period 2) Additional Analyses

The following analyses will be done for all four randomized treatment groups in the FAS:

- Proportion with at least 3 points reduction from baseline in NRS in Patient Global Assessment of Skin Pain at its worst, among subjects with baseline NRS ≥ 4, at weeks 24 and 32 will be summarized by number and proportion along with Clopper-Pearson 95% CI without strata according to the four randomized treatment groups.
 - NRI will be handled analogously to the corresponding secondary endpoint analysis, except subjects who took Tramadol as allowed per-protocol (at a dose of up to 100 mg po every 4 hours, not to exceed 400 mg per 24 hours) during the 28 days prior to the visit will not be counted as a non-responder.
- Descriptive MMRM analyses will be performed by randomized treatment group, for the continuous endpoints described below. The measured value at the visit will be used as the response variable, with visit week, treatment, and treatment * visit week interaction included as predictors. The model will include all visits from Day 1 through Week 32. Unstructured covariance matrix will be used. Other variance-covariance matrices, such as autoregressive, and compound-symmetric will be considered if the model does not converge. Estimated LSMean, corresponding SE values, and 95% confidence intervals will be summarized at the timepoints defined below.
 - Modified Sartorius Score at Weeks 24 and 32;
 - NRS PGA of Skin Pain (at its worst and average respectively) at Weeks 24 and 32. To maintain consistency between all visits, only the score collected on the visit day will be used for this analysis.
 - Draining fistula count at Weeks 24 and 32;
 - EQ-5D at Weeks 24 and 32;
 - DLQI at Weeks 24 and 32;
 - HADS, HADS-anxiety, and HADS-depression at Weeks 24 and 32;
 - IHS4 scores at Weeks 24, and 32

These summaries will address the question of expected results if a subject is assigned to either 32 weeks of izokibep or 16 weeks of placebo followed by 16 weeks of izokibep.

- A time-to-event analysis using Kaplan-Meier (KM) curves by randomized treatment group will be created for the events listed below.). If estimable, quartiles of the time to each event will be summarized by randomized treatment group. Product limit estimate at Week 32 (Day 224) will be provided. Participants will be censored at the time of last recorded assessment on study:
 - First achievement of HiSCR75
 - First achievement of HiSCR100

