6.7. Safety

For all Safety Tables, data in Part A and Part B will be summarized as follows, unless otherwise specified:

- Part A summarized with all subjects for the entire time (Week 0 to Week 32)
- Part B, for Period 1, will include the first 16 weeks until the first dose of treatment administered in Period 2 at or after Week 16, summarized by the randomized treatment arms and the combined placebo group (Placebo QW/ Placebo Q2W; Izokibep QW; Izokibep Q2W), and includes all subjects who received at least one dose of study treatment. AEs will be included if date of onset is on or after the day of the first dose received in Period 1 and before the date of the first dose received in Period 2. If a subject did not receive any dose of study treatment in Period 2, all AEs with onset on or after the day of first dose received in Period 1 through 4 weeks (28 days) after the last dose received will be included.
- Part B, Period 2, will include data collected on and after the first dose of study treatment administered at Week 16 visit (or after Week 16 visit, if Week 16 visit is missing), summarized by the randomized treatment groups (Placebo Izokibep QW; Placebo Izokibep Q2W; Izokibep QW; Izokibep Q2W), and includes all subjects who took at least one dose of study treatment in Period 2. AEs will be included if date of onset is on or after the day of first dose received in Period 2 through 4 weeks (28 days) after the last dose received.

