 - One table presented for each treatment arm (160 mg QW / 160 mg Q2W / combined placebo)
- Treatment period 2
 - Baseline prior to treatment period 1 (meet Hy's Law / not meet Hy's Law)
 - Any time during period 2 (meet Hy's Law at least one time / not meet Hy's Law at any time)
 - One table presented for each treatment arm (160 mg QW / 160 mg Q2W / placebo 160 mg QW / placebo 160 mg Q2W)

Separate Kaplan Meier (KM) analyses plots will be created for time to:

- First instance of meeting Hy's Law
- First instance of ALT or AST $\geq 5 \times ULN$
- First instance of ALT or AST \ge 3 x ULN and total bilirubin \ge 2 x ULN (>35% direct bilirubin) simultaneously

- First instance of ALT or AST \geq 3 x ULN and international normalized ratio (INR) \geq 1.5 simultaneously
- First instance of ALT or AST $\ge 3 \times ULN$ associated with symptoms (new or worsening) believed to be related to liver injury or hypersensitivity at any time

for the study duration (Day 1 through Week 32). In each plot, the subjects taking any treatment with Q2W frequency will be indicated by a solid line. The subjects taking any treatment with QW frequency will be indicated by a dashed line. Separate colors will be used to distinguish subjects randomized to izokibep and those randomized to placebo.

Subjects who do not experience an event will be censored at their last attended assessment. The date/time of onset of the first instance of the event of interest will be used as the date/time of the event in the analysis.

The product-limit estimator at Week 16 and Week 32 will be summarized by treatment group.

If there are < 3 events in a treatment arm for an event, then the KM analysis will not be done.

A listing of all LFT results from all subjects who meet Hy's Law at least one time during the study will be produced, sorted by subject and date. This listing will show subject, treatment assignment, period, ALT, AST, ALP, bilirubin and INR.

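### As worded, one sparse arm cancels the whole Kaplan-Meier onset analysis for an AESI category or liver event; only descriptive output is affected

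*SAP*

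**What the plan says.** SAP 6.7.2 states the purpose of the plots: "To assess the pattern of initial onset, AESIs and ISRs will also be presented by Kaplan-Meier plot". They are planned for the full study and, separately, for Period 2, with estimates by group: "The product limit estimator will be presented by treatment group for Week 4 (Day 28" and at later time points to Week 32. For AESI categories the condition is: "If an AESI category has < 3 events in a treatment arm, then this analysis will not be done". The injection-site-reaction plot in the same section carries no such condition.

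SAP 6.7.3.1 plans similar plots for five liver events from Day 1 to Week 32, again with a condition: "If there are < 3 events in a treatment arm for an event, then the KM analysis will not be done". Each liver plot shows the arms together, with line style for dosing frequency and colour for randomized treatment: "Separate colors will be used to distinguish subjects randomized to izokibep and those randomized to placebo".

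The arms being counted are not fixed in one place:

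- SAP 6.7 sets out Period 2 safety data as "summarized by the randomized treatment groups (Placebo Izokibep QW; Placebo Izokibep Q2W; Izokibep QW; Izokibep Q2W", which is four groups.
- The Period 1 Hy's Law tables in SAP 6.7.3.1 use the word arm for three groups: "One table presented for each treatment arm (160 mg QW / 160 mg Q2W / combined placebo".
- For the study-duration AESI plot, SAP 6.7.2 refers only to treatment group.

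The efficacy Kaplan-Meier analysis in SAP 6.6.7 treats sparse data more narrowly. Curves are drawn for every randomized group and only the quartiles are conditional: "If estimable, quartiles of the time to each event will be summarized by randomized treatment group".

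**The concern.** A minimum event count is reasonable when a category is rare everywhere, because the curves would show almost nothing. The difficulty is that the rule is triggered by the sparsest arm and then applies to all of them. The placebo-randomized groups are half the size of the izokibep groups and spend only half the treatment period on izokibep. If izokibep raises the risk of an event, those groups are the likely sparse ones, and the display disappears where a comparison of onset would be most informative.

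At stake is the planned AESI and liver output that accounts for time at risk. Crude incidence tables ignore follow-up time, and listings give start days without a population at risk. Whether the output appears would depend on the count in the smallest arm and on whether placebo is counted as one group or two.

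**Working it through.** The plan gives no figure for how often the rule would apply, so there is none to reproduce. The check has two parts.

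**Reading.** Both sentences name one arm as the trigger and the analysis as what is dropped. Neither limits the consequence to that arm, and neither requires all arms to be sparse. Since the arms share a plot, cancelling the analysis removes the izokibep curves too.

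**Size.** Inputs:

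- Group sizes of 57, 57, 28 and 28, which sum to 170 and lie within the ranges in SAP 2.1 (56–57 and 28–29). Combined placebo is 28 + 28 = 56.
- Event rates are assumptions, shown from 1% to 20%.
- The count is of subjects with an event, taken as binomial and independent between groups.

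Let a, b and c be the probability of at least 3 subjects with an event among 57, 28 and 56. The case of interest is that both izokibep groups reach 3 but the analysis is cancelled:

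- four groups: a² × (1 − b²)
- combined placebo: a² × (1 − c)

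| Equal rate | a | b | c | Four groups | Combined placebo |
|---|---|---|---|---|---|
| 1% | 0.0196 | 0.0027 | 0.0187 | 0.04% | 0.04% |
| 2% | 0.1059 | 0.0180 | 0.1018 | 1.1% | 1.0% |
| 3% | 0.2442 | 0.0506 | 0.2362 | 5.9% | 4.6% |
| 5.1% | 0.5654 | 0.1717 | 0.5533 | 31.0% | 14.3% |
| 10% | 0.9334 | 0.5406 | 0.9281 | 61.7% | 6.3% |
| 15% | 0.9942 | 0.8129 | 0.9934 | 33.5% | under 1% |
| 20% | 0.9997 | 0.9388 | 0.9996 | 11.9% | 0.04% |

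For example, at 10% with four groups: 0.9334² × (1 − 0.5406²) = 0.617.

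**Unequal rates.** Suppose izokibep has a 10% rate by Week 32 at constant hazard, and placebo carries no risk until the switch at Week 16. The placebo-randomized rate is then 1 − 0.9^0.5 = 0.0513.

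- Four groups: 0.9334² × (1 − 0.1717²) = 0.845.
- Combined placebo: 0.9334² × (1 − 0.5533) = 0.389.

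**Period 2.** Suppose all four groups are on izokibep at 5.1% and every subject continues.

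- Produced under the literal rule: 0.5654² × 0.1717² = 0.009.
- Produced if one group with 3 or more is enough: 1 − (1 − 0.5654)² × (1 − 0.1717)² = 0.870.

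At equal rates of 1% and 2% the one-group condition produces the analysis only 4.4% and 22.9% of the time, so very rare categories gain little.

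**The case against.** The strongest reply is that the rule should be read arm by arm. A Kaplan-Meier curve is estimated separately in each group, no between-arm test is planned for these plots, and the estimates are presented by group. Skipping only the sparse arm's curve would be a natural convention. That reading is possible, but the text does not state it and a programmer would have to supply it.

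Layout is also delegated to the table, figure and listing shells (SAP 6.1), which are not among the documents here. They may settle how sparse arms are drawn, but they cannot be assumed to override an explicit SAP sentence. On grouping, four groups is the sensible inference for these plots, since they run past the Week 16 switch and the liver styling implies four. The three-group usage belongs to a Period 1 table. It remains an inference, and SAP 6.1 also lists a combined-placebo group among its labels.

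The objection on rates stands in part. The high probabilities need an incidence of roughly 5–10% or more within one category. Protocol 2.3.1 says the class effects have not been identified with izokibep, and Protocol 5.2 excludes subjects with raised transaminases at screening. For tuberculosis, malignancy or Hy's Law, 1–2% may be the more relevant part of the range, and there the problem almost vanishes.

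The unit also matters. The SAP counts events and the working counts subjects. If repeat events count, every group reaches 3 more often, and the net effect on the probabilities has no fixed direction. For a first-onset analysis, subjects with a first event is the right unit, but adopting it changes the rule and should be stated.

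A reader might infer that the rule could hide a safety signal. The documents do not support that. AESI tables by group and period, listings with relative start day, the listing of possible drug-induced liver injury and the Hy's Law shift tables (SAP 6.7.2 and 6.7.3.1) do not depend on the rule, and Protocol 9.3.5 plans no safety p-values.

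**Conclusion.** The point holds as a cheap improvement of minor weight. Read literally, both sentences let one sparse arm cancel the onset analysis for arms that have enough events. The loss is confined to descriptive plots and product-limit estimates. No hypothesis test, error rate or sample size is touched.

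The size depends entirely on assumed rates and on the grouping. It is negligible at 1–2%. From about 5% to 10% with equal rates it rises from 31% to 62% with four groups and falls from 14% to 6% with combined placebo. With 10% on izokibep and 5.1% in the placebo-randomized groups it is 84.5% or 38.9%. These figures assume binomial counts of subjects and the planned group sizes; the Period 2 figure also assumes that all subjects continue. None of them is a forecast for a particular category.

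**What to change.** Replace both sentences with:

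*The Kaplan-Meier analysis is produced for a category when at least one treatment group has 3 or more subjects with a first event; curves and product-limit estimates are then shown for all groups. For Part B the groups are the four randomized groups; for Part A, the single arm.*

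Apply the same condition to the product-limit sentences in SAP 6.7.2 and 6.7.3.1, and state that the count is now of subjects with a first event. Part A is named because SAP 6.7 applies the safety outputs to it as well.

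The cost is two replaced sentences and one added condition, made before unblinding so that the choice of plots does not follow sight of counts by arm. The downside is a few more plots, some with flat curves for groups with 0 to 2 events.

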4.1.2. Part B: Randomized, Double-blind, Dose-finding

Part B is a randomized, double-blind, placebo-controlled, parallel-group, dose-finding investigation to evaluate the efficacy, safety, and immunogenicity of izokibep in subjects with moderate to severe HS. Subjects will complete up to a 28-day screening period, followed by a 16-week double-blind treatment period. At completion of the Week 16 visit procedures, subjects randomized to placebo will be switched to active treatment in a blinded manner for the Week 16 dose through Week 30 (Q2W dose group) or Week 31 (QW dose group). Subjects randomized to izokibep will remain on the same dose through Week 30 (Q2W dose group) or Week 31 (QW dose group). After their respective treatment periods, all subjects will enter a follow-up period that includes 2 visits to be completed at Week 39 and Week 45. For subjects who early terminate, the follow-up visits should be completed 8 weeks (± 5 days) and 14 weeks (± 5 days) after the last dose of study drug.

Approximately 170 subjects will be randomized into 1 of 4 groups in a 1:1:2:2 ratio as follows:

- Group 1 (n = 28-29): placebo SC QW from Day 1 (Week 0) to Week 15, then izokibep SC 160 mg QW from Week 16 to Week 31.
- Group 2 (n = 28-29): placebo SC Q2W from Day 1 (Week 0) to Week 14, then izokibep SC 160 mg Q2W from Week 16 to Week 30.
- Group 3 (n = 56-57): izokibep SC 160 mg QW from Day 1 (Week 0) to Week 31.
- Group 4 (n = 56-57): izokibep SC 160 mg Q2W from Day 1 (Week 0) to Week 30.

Randomization will be stratified by any prior biologic/Janus Kinase (JAK) inhibitor use for HS (Yes/No) and Hurley Stage (II or III).

Subjects will complete study assessments according to the study visits outlined in the SoA.

Subjects in the QW dosing groups (Group 0 [Part A], Groups 1 and 3 [Part B]) will have study visits at screening, Day 1 (Week 0), and at Weeks 1, 2, 3, 4, 8, 12, 13, 14, 15, 16, 17, 20, 24, 28, and 32 as well as at the follow-up visits.

Subjects in the Q2W dosing regimens (Groups 2 and 4 in Part B) will have study visits at screening, Day 1 (Week 0), and at Weeks 2, 4, 8, 12, 14, 16, 18, 20, 24, 28, and 32 as well as at the follow-up visits.

Subjects assigned to placebo SC QW and placebo SC Q2W will be grouped together into a single placebo group for comparison to each dosing regimen of izokibep for Part B. The primary endpoint will be assessed at Week 16.

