7.1. Discontinuation of Study Drug

In rare instances, it may be necessary for a subject to permanently discontinue study drug. The reason for the permanent discontinuation of study drug will be documented. If study drug is permanently discontinued, the subject will be encouraged to remain in the study to be evaluated for safety and efficacy. Subjects should continue to complete study assessments as outlined in the SoA where possible, with the exception of study drug administration. Reasons for removal from study drug include any of the following:

- subject request
- safety concern (eg, due to an AE, ineligibility determined, protocol deviation, non-compliance, pregnancy, hepatotoxicity)
- death
- lost to follow-up
- decision by sponsor (other than subject request, safety concern, lost to follow-up)
- protocol-specified reasons:
 - o A subject who requires more than 2 lesion interventions within the first 16 weeks of the study must be discontinued from study drug
 - After Week 16, a subject who requires more than 2 lesion interventions within a
 4-week period or has 2 of the same interventions on the same lesion within that
 period must be discontinued from study drug

Additionally, subjects experiencing any of the following AEs must be discontinued from study drug, but continued in the study and followed until resolution of the AE:

- Hematologic AE of moderate or severe intensity (refer to Section 10.3.3 for description of intensity assessment)
- Cardiovascular AE of moderate or severe intensity

Note: Exceptions to this requirement include the following specific cardiovascular events that represent asymptomatic findings discovered as part of testing that may have been done for other reasons most likely unrelated to the drug product or the trial itself. Cardiovascular AEs that do not meet study drug discontinuation criteria include the following AEs related to asymptomatic valvular findings and asymptomatic arrythmia findings:

- o Valvular asymptomatic findings:
 - Aortic valve: Asymptomatic valvular thickening with or without mild valvular regurgitation or stenosis by imaging
 - Mitral valve disease: Asymptomatic; moderate regurgitation or stenosis by imaging

- Pulmonary valve disease: Asymptomatic; moderate regurgitation or stenosis by imaging
- Tricuspid valvular disease: Asymptomatic; moderate regurgitation or stenosis by imaging
- o Arrythmia findings of a non-urgent medical nature:

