5.1.3. Treatment Period

Data collected on Day 1 will be assigned to the Treatment Period unless the time (HH:MM) of data collection and time (HH:MM) of the first dose of study drug are both recorded and the data collection time is before the time of the first dose of study drug. In this case, the assessment will be assigned to the screening period. If the time (HH:MM) of data collection is not recorded but the protocol and/or CRF includes an instruction to the effect that all Day 1 assessments are to be performed prior to the first dose of study drug, the data collected at Day 1 will be assigned to the screening period. However, adverse events and concomitant medications starting on Day 1, will be assigned to the Treatment Period, unless the time (HH:MM) demonstrates otherwise.

The Treatment Period is defined as the period from the date/time of the first dose of study drug to Week 32 (four weeks after the last dose) or early termination/end of treatment visit (within two weeks from the last dose).

Treatment will be divided into two periods, Period 1 and Period 2. In Part B, Period 1 will start at the first dose of study drug and end at Week 16 when Week 16 assessments are completed and before administration of study drug. Period 2 will start at the time of first administration of study drug at or after Week 16 and end at Week 32 or early termination/end of treatment visit.

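### The Kaplan-Meier analysis of events of special interest keeps subjects at risk until last contact, past the window in which events are collected and counted, so its estimates run modestly low

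*SAP*

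**What the plan says.** SAP 6.7.2 plans Kaplan-Meier plots of time to first event in each AESI category, for the full study and for Period 2. Product-limit estimates are reported by treatment group every 4 weeks from Week 4 to Week 32. A category with fewer than 3 events in an arm is not analysed. The censoring rule is: "Subjects who do not experience an event will be censored at their date of last contact". The SAP does not define the date of last contact.

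Three windows bear on which events can enter the curve:

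- **Collection (SAP 6.7.2; Protocol 8.3.1 agrees).** "All AEs will be collected from the first dose of study drug until 4 weeks after the last dose of study drug". For serious events: "All SAEs will be collected from the signing of the ICF until the 8-week follow-up visit".
- **Counting in safety summaries (SAP 6.7).** For a subject with no Period 2 dose, AEs "through 4 weeks (28 days) after the last dose received will be included". The Period 2 rule also ends 28 days after the last dose.
- **Treatment-emergent definition (SAP 6.7.2).** Events count "up to 4 weeks after the end of the Treatment Period". SAP 5.1.3 ends that period at Week 32 or at an early termination visit within two weeks of the last dose.

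Contact can outlast all three. Protocol 4.1.2 gives early terminators a final visit "14 weeks (± 5 days) after the last dose of study drug". For those who stop only the drug, Protocol 7.1 says: "If study drug is permanently discontinued, the subject will be encouraged to remain in the study to be evaluated for safety and efficacy". Their schedule can run to Week 45.

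**The concern.** A product-limit estimate divides events by the number at risk, so a subject should be in the denominator only while an event would be seen and counted. Here the numerator closes at about 4 weeks after the last dose, while the denominator stays open until last contact. The extra time is event-free by construction for non-serious events, and the resulting error makes the product look safer.

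Events of interest are part of the Part B secondary safety objective, and these estimates are the planned description of when such events begin. The injection-site-reaction curves in the same section are censored at the last injection, so they do not carry this extra time.

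**Working it through.** The plan states no AESI rate, stopping rate or Kaplan-Meier estimate, so there is no figure of its own to reproduce.

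**Timeline, from the documents' windows**

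| Last dose (week) | Non-serious AE collection ends | Last contact at +14 weeks | Unobserved weeks at risk before Week 32 | Same, if the subject stays in the study |
|---|---|---|---|---|
| 8 | 12 | 22 | 10 | 20 |
| 12 | 16 | 26 | 10 | 16 |
| 16 | 20 | 30 | 10 | 12 |
| 20 | 24 | 34 | 8 | 8 |
| 24 | 28 | 38 | 4 | 4 |
| 28 | 32 | 42 | 0 | 0 |

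Completers have their last dose at Week 30 (Q2W) or 31 (QW), so collection covers them to Week 34 or 35. Only subjects whose last dose is before about Week 28 affect the estimates through Week 32.

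**Expected estimate.** Assumptions, none from the documents: a constant hazard λ, the same on and off drug; 10%, 20% or 30% stop drug, with last dose uniform over Weeks 4-12; stopping unrelated to AESI risk. For a true Week 32 incidence of 10%, λ = −ln(0.90)/32 = 0.00329 per week.

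Let A(t) be the share at risk whose events are still collected, and P(t) the share kept at risk past the collection window. The curve then follows hazard h(t) = λ·A(t)/(A(t)+P(t)), and the estimate is 1 − exp(−∫h dt) over Weeks 0 to 32.

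Hand check, 20% all stopping at Week 8:

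- With contact to Week 22, Weeks 0-12 carry the full hazard, Weeks 12-22 about 0.8 of it, and Weeks 22-32 the full hazard. That is 12 + 0.8×10 + 10 = 30 effective weeks, so 1 − exp(−0.00329×30) = 9.4%.
- With contact past Week 32, it is 12 + 0.8×20 = 28 effective weeks, which gives 8.8%.

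Integration with last doses spread over Weeks 4-12, true value 10%:

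| Share stopping | 4-week window, contact +14 weeks | 4-week window, stays in study | 8-week window, contact +14 weeks | 8-week window, stays in study | Censor at last dose + 28 days |
|---|---|---|---|---|---|
| 10% | 9.69 | 9.39 | 9.82 | 9.51 | 10.00 |
| 20% | 9.38 | 8.77 | 9.62 | 9.03 | 10.00 |
| 30% | 9.05 | 8.16 | 9.42 | 8.54 | 10.00 |

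The 8-week columns treat every AESI as serious and counted to the 8-week visit. With a true 5%, the 4-week window gives 4.8-4.5% (contact to 14 weeks) or 4.7-4.1% (stays in the study). With a true 20% it gives 19.4-18.2% or 18.8-16.4%.

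At Week 16, the last placebo-controlled timepoint, the same 10% hazard corresponds to a true 5.1%. The SAP rule reads 5.0-4.8% there.

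**The case against.** The case for leaving the rule alone has several parts.

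*Late events can still be recorded.* This is partly right. Serious events are collected to the 8-week visit, and some AESI categories are serious by definition or usually so. Protocol 8.2.5 also asks for clinically significant laboratory changes during the study to be recorded as AEs, and hematology is drawn at Week 39, which may bring in some late cytopenias. So a reader should not infer that no AESI can be recorded after 4 weeks. The mismatch remains: 14 weeks exceeds 8, Candida infection and cytopenias need not be serious, and SAP 6.7 leaves out anything after 28 days.

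*The treatment-emergent window is longer.* For an early terminator it reaches at most about 2 + 4 = 6 weeks after the last dose. For someone who stays in the study it may reach beyond Week 32. A longer counting window cannot restore non-serious events that were never collected.

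*The effect is small and descriptive.* This stands. Protocol 9.3.5 plans no p-values for safety. In an arm of 56, one subject is 1/56 = 1.8 points, and the binomial standard error at 10% is √(0.1×0.9/56) = 4.0 points. Most scenarios at 10% move the estimate by less than one subject.

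*The arms are compared fairly.* A reader might infer that the rule distorts the comparison between arms. The documents do not show that; it would need early stopping to differ between arms, and they give no stopping rates. After Week 16 every arm is on izokibep, so Week 32 is not a placebo comparison.

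**Conclusion.** The point holds for the AESI product-limit estimates. As written, the rule counts time at risk in which non-serious events are no longer collected, and neither document caps that time. The bias is downward in every scenario tried and modest: on a true 10%, from about 0.2 points (10% stopping, 8-week window, contact to 14 weeks) to 1.8 points (30% stopping, 4-week window, subjects staying in the study).

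It would be tempting to conclude that AESI incidence in general is understated. That does not follow: the counts and percentages by period, system organ class and preferred term do not use this risk time and are unaffected. No hypothesis test, alpha allocation or efficacy result is touched.

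The direction follows from the documents. The size rests on assumed stopping and event rates, a constant hazard, and reading last contact as the 14-week visit or later.

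**What to change.** In SAP 6.7.2, for the full-study and Period 2 AESI curves:

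1. Censor event-free subjects at the earlier of last contact and last dose + 28 days, and define the date of last contact.
2. Apply the same cut-off to events. A first event after that date is not counted in the curve and is listed separately.
3. Reconcile the 28-day window in SAP 6.7 with the treatment-emergent window in SAP 6.7.2, so that one window governs both events and risk time.

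This takes a short text change and one derivation, with no new data. The cost is slightly fewer subjects at risk at late weeks, and serious AESIs recorded 4 to 8 weeks after the last dose would appear only in listings. The revised estimate is unbiased only if stopping is non-informative. Protocol 7.1 requires stopping for certain adverse events, so the report should state that limitation beside the curves.
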